The number (and proportion) of subjects with AESI/related to identified and potential risks (see Section 10.1) will be summarized by treatment.

A subject with multiple adverse events within a primary system organ class is only counted once towards the total of the primary system organ class.

Vital signs

All vital signs data will be listed by treatment group, subject, and visit/time and if ranges are available, abnormalities (and relevant orthostatic changes) will be flagged. Summary statistics will be provided by treatment and visit/time.

12-lead ECG

PR, QRS, QT, QTcF, and RR intervals will be obtained from 12-lead ECGs for each subject during the study. ECG data will be read and interpreted (centrally/locally).

All ECG data will be listed by treatment group, subject and visit/time, abnormalities will be flagged. Summary statistics will be provided by treatment and visit/time.

Clinical laboratory evaluations

All laboratory data will be listed by treatment group, subject, and visit/time and if normal ranges are available abnormalities will be flagged. Summary statistics will be provided by treatment and visit/time. Shift tables using the low/normal/high/ (low and high) classification will be used to compare baseline to the worst on-treatment value.

Grading of laboratory values will be assigned programmatically as per NCI Common Terminology Criteria for Adverse Events (CTCAE) version 5.0 or current version. The calculation of CTCAE grades will be based on the observed laboratory values only, clinical assessments will not be taken into account.

CTCAE Grade 0 will be assigned for all non-missing values not graded as 1 or higher. Grade 5 will not be used.

For laboratory tests where grades are not defined by CTCAE, results will be categorized as low/normal/high based on laboratory normal ranges.

The following summaries will be generated separately for hematology, and biochemistry tests:

- 1. Listing of all laboratory data with values flagged to show the corresponding CTCAE grades if applicable and the classifications relative to the laboratory normal ranges
- 2. For laboratory tests where grades are defined by CTCAE,
- 3. Worst post-baseline CTCAE grade (regardless of the baseline status). Each subject will be counted only once for the worst grade observed post-baseline.
- 4. Shift tables using CTCAE grades to compare baseline to the worst on-treatment value
- 5. For laboratory tests where grades are not defined by CTCAE,

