- Listing of all CTC grade 3 or 4 laboratory toxicities

Liver toxicity parameters

Liver parameters of interest are Total Bilirubin (TBIL), Alanine Transaminase (ALT), Aspartate Aminotransferase (AST) and Alkaline Phosphatase (ALP). The number (%) of patients with peak post-baseline values and combined elevations post-baseline will be summarized as follows:

- ALT > 3x ULN, 5x ULN, 20x ULN
- AST > 3x ULN, 5x ULN, 20x ULN
- ALT or AST > 3x ULN, 5x ULN, 20x ULN
- ALP \geq 2x ULN, 3x ULN, 5x ULN, 8xULN, 10x ULN
- TBIL > 2xULN, 3x ULN, 5xULN, 10x ULN

For the following combined categories, the assessments need not be concurrent, i.e., participants are counted based on the most extreme value for each parameter.

If AST and ALT \leq ULN at baseline:

- ALT or AST $>3x$ ULN & TBL $>2x$ ULN
- ALT or AST $>3x$ ULN & TBL $>2x$ ULN & ALP $\geq 2x$ ULN
- ALT or AST $>3x$ ULN & TBL $>2x$ ULN & ALP $<2x$ ULN

If AST or ALT $>$ ULN at baseline

- Elevated ALT or AST ($>3x$ Baseline value or $8x$ ULN) and TBIL ($>2x$ Baseline value and $2x$ ULN)
- Elevated ALT or AST ($>3x$ Baseline value or $8x$ ULN) and TBIL ($>2x$ Baseline value and $2x$ ULN) and ALP $\geq 2x$ ULN
- Elevated ALT or AST ($>3x$ Baseline value or $8x$ ULN) and TBIL ($>2x$ Baseline value and $2x$ ULN) and ALP $<2x$ ULN

Further medical review has to be conducted to assess potential confounding factors such as, liver metastases, liver function at baseline etc.

A figure displaying time course of hepatic injury tests (ALT, AST, TBL, ALP) in patients with Hy's law will be displayed in the Safety Set. Additionally, evaluation of Drug-Induced Serious Hepatotoxicity (eDISH) plots will be produced to display ALT and AST values by TBL values in units of ULN.

Depending on availability of data, plots of hepatic tumor volume against ALT, AST, or TBL values in units of ULN may be generated.

Separate displays will be generated for the randomized period, cross-over period, and re-treatment period.

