5.3 Laboratory parameters derivations

Grade categorization of lab values will be assigned programmatically as per NCI Common Terminology Criteria for Adverse Events (CTCAE) version 5.0 or current. The calculation of CTCAE grades will be based on the observed laboratory values only, clinical assessments will not be taken into account. The criteria to assign CTCAE grades are given in Novartis internal criteria for CTCAE grading of laboratory parameters shown below.

For laboratory tests where grades are not defined by CTCAE v5.0, results will be graded by the low/normal/high based on laboratory normal ranges.

A severity grade of 0 will be assigned for all non-missing lab values not graded as 1 or higher. Grade 5 will not be used. For laboratory tests that are graded for both low and high values, summaries will be done separately and labelled by direction, e.g., sodium will be summarized as hyponatremia and hypernatremia.

CTC grades for laboratory values in Novartis Oncology (based on CTCAE v5 – Nov 2017)

Page 1

CTC Grades ⁽¹⁾									
Lab test (toxicity)	SI unit	Lab test (NCDS)	Normal ranges (Merck manual, July 2015) and conversion factors	0	1	2	3	4	
Hematology									
WBC ↓ WBC (Leukocytosis)	$10^9/L$ $10^9/L$	WBC WBC	3.9 – 10.7 $\times 10^9/L$	≥ LLN	< LLN - 3.0 $\times 10^9/L$ -	< 3.0 – 2.0 $\times 10^9/L$ -	< 2.0 – 1.0 $\times 10^9/L$ > 100 $\times 10^9/L$	< 1.0 $\times 10^9/L$ -	
Hemoglobin (Anemia)	g/L	HGB	120 - 160 g/L or 7.4 - 9.9 mmol/L (F) 140 - 170 g/L or 8.7 - 10.6 mmol/L (M) (16.113 \times mmol/L = g/L)	≥ LLN	< LLN - 100 g/L < LLN - 6.2 mmol/L Increase >20 g/L above ULN	< 100 - 80 g/L < 6.2 - 4.9 mmol/L Increase >20-40 g/L above ULN	< 80 g/L < 4.9 mmol/L Increase >40 g/L above ULN	-	
Platelets ↓	$10^9/L$	PLAT	150 - 350 $\times 10^9/L$	≥ LLN	< LLN - 75.0 $\times 10^9/L$	< 75.0 - 50.0 $\times 10^9/L$	< 50.0 - 25.0 $\times 10^9/L$	< 25.0 $\times 10^9/L$	
Neutrophils ↓	$10^9/L$	NEUT			$\geq 2 \times 10^9/L$	$< 2.0 - 1.5 \times 10^9/L$	$< 1.5 - 1.0 \times 10^9/L$	$< 1.0 - 0.5 \times 10^9/L$	
Lymphocytes ↓ Lymphocytes ↑	$10^9/L$ $10^9/L$	LYM LYM		$\geq 1.5 \times 10^9/L$	$< 1.5 - 0.8 \times 10^9/L$ -	$< 0.8 - 0.5 \times 10^9/L$ -	$< 0.5 - 0.2 \times 10^9/L$ $> 4 - 2 \times 10^9/L$	$< 0.2 \times 10^9/L$ -	
Biochemistry									
AST ↑	U/L	AST	0 - 35 U/L or 0 - 0.58 kat/L ($60 \times \text{ukat}/L = U/L$)	≤ ULN	> ULN - 3.0 \times ULN	> 3.0 - 5.0 \times ULN	> 5.0 - 20.0 \times ULN	> 20.0 \times ULN	

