Calcium (corrected) (Hypercalcemia)	mmol/L	CACALC	2.2 - 2.6 mmol/L or 9 - 10.5 mg/dL ($0.2495 \times \text{mg/dL} = \text{mmol/L}$)	≤ ULN	> ULN - 11.5 mg/dL > ULN - 2.9 mmol/L	> 11.5 - 12.5 mg/dL > 2.9 - 3.1 mmol/L	> 12.5 - 13.5 mg/dL > 3.1 - 3.4 mmol/L	> 13.5 mg/dL > 3.4 mmol/L	
Calcium (corrected) (Hypocalcemia)	mmol/L	CACALC		≥ LLN	< LLN - 8.0 mg/dL < LLN - 2.0 mmol/L	< 8.0 - 7.0 mg/dL < 2.0 - 1.75 mmol/L	< 7.0 - 6.0 mg/dL < 1.75 - 1.5 mmol/L	< 6.0 mg/dL < 1.5 mmol/L	
Magnesium (Hypermagnesemia)	mmol/L	MG	0.62 - 0.99 mmol/L or 1.5 - 2.4 mg/dL ($0.4114 \times \text{mg/dL} = \text{mmol/L}$)	≤ ULN	> ULN - 3.0 mg/dL > ULN - 1.23 mmol/L	-	> 3.0 - 8.0 mg/dL > 1.23 - 3.3 mmol/L	> 8.0 mg/dL > 3.3 mmol/L	
Magnesium (Hypomagnesemia)	mmol/L	MG		≥ LLN	< LLN - 1.2 mg/dL < LLN - 0.5 mmol/L	< 1.2 - 0.9 mg/dL < 0.5 - 0.4 mmol/L	< 0.9 - 0.7 mg/dL < 0.4 - 0.3 mmol/L	< 0.7 mg/dL < 0.3 mmol/L	
Glucose (non-fasting) (Hyperglycemia)	mmol/L	GLUCSN	< 7.8 mmol/L or < 140 mg/dL ($0.05551 \times \text{mg/dL} = \text{mmol/L}$)		Defined by clinical criteria only in CTCAE V5				
Glucose (fasting) (Hyperglycemia)	mmol/L	GLUCSF	3.9 - 5.8 mmol/L or 70 - 105 mg/dL ($0.05551 \times \text{mg/dL} = \text{mmol/L}$)		Defined by clinical criteria only in CTCAE V5				
Glucose (Hypoglycemia)	mmol/L	GLUCSN/ GLUCSF		≥ LLN	< LLN - 55 mg/dL < LLN - 3.0 mmol/L	< 55 - 40 mg/dL < 3.0 - 2.2 mmol/L	< 40 - 30 mg/dL < 2.2 - 1.7 mmol/L	< 30 mg/dL < 1.7 mmol/L	
Potassium (Hyperkalemia)	mmol/L	K	3.5 - 5.0 mmol/L ($0.2558 \times \text{mg/dL} = \text{mEq/L} = \text{mmol/L}$)	≤ ULN	> ULN - 5.5 mmol/L	> 5.5 - 6.0 mmol/L	> 6.0 - 7.0 mmol/L	> 7.0 mmol/L	
Potassium (Hypokalemia)	mmol/L	K		≥ LLN	< LLN - 3.0 mmol/L	-	< 3.0 - 2.5 mmol/L	< 2.5 mmol/L	
Sodium (Hypernatremia)	mmol/L	SODIUM	136 - 145 mmol/L ($0.435 \times \text{mg/dL} = \text{mEq/L} = \text{mmol/L}$)	≤ ULN	> ULN - 150 mmol/L	> 150 - 155 mmol/L	> 155 - 160 mmol/L	> 160 mmol/L	
Sodium (Hyponatremia)	mmol/L	SODIUM		≥ LLN	< LLN - 130 mmol/L	< 129 - 125 mmol/L	< 124 - 120 mmol/L	< 120 mmol/L	
Triglyceride ↑	mmol/L	TRIG	< 2.82 mmol/L or < 250 mg/dL ($0.01129 \times \text{mg/dL} = \text{umol/L}$)	< 150 < 1.71	≥ 150 - 300 mg/dL ≥ 1.71 - 3.42 mmol/L	> 300 - 500 mg/dL ≥ 3.42 - 5.7 mmol/L	> 500 - 1000 mg/dL ≥ 5.7 - 11.4 mmol/L	> 1000 mg/dL ≥ 11.4 mmol/L	
Coagulation									
INR↑	1	INR	0.8 - 1.2	≤ 1.2	> 1.2 - 1.5	> 1.5 - 2.5	> 2.5	-	
Activated partial thromboplastin time↑	sec	APTT	25 - 35 sec	≤ ULN	> ULN - 1.5 \times ULN	> 1.5 - 2.5 \times ULN	> 2.5 \times ULN	-	

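### The SAP hyponatremia row leaves sodium from 129 to under 130 and from 124 to under 125 mmol/L ungraded, and the default rule then makes those values Grade 0

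*SAP*

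**What the plan says.** SAP 5.3 has grades assigned by program: "Grade categorization of lab values will be assigned programmatically as per NCI Common Terminology Criteria for Adverse Events (CTCAE) version 5.0 or current". It names the table printed in that section as the source of the cut-offs: "The criteria to assign CTCAE grades are given in Novartis internal criteria for CTCAE grading of laboratory parameters shown below".

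The hyponatremia row of that table reads:

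- Grade 0: at or above the lower limit of normal (LLN), with 136 mmol/L shown as the lower end of the normal range
- Grade 1: "< LLN - 130 mmol/L"
- Grade 2: "< 129 - 125 mmol/L"
- Grade 3: "< 124 - 120 mmol/L"
- Grade 4: below 120 mmol/L

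For values that match no cell, SAP 5.3 states: "A severity grade of 0 will be assigned for all non-missing lab values not graded as 1 or higher". Protocol 12.5.3 has the same default: "CTCAE Grade 0 will be assigned for all non-missing values not graded as 1 or higher".

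SAP 2.8.3 uses these grades for the worst post-baseline grade table, for shift tables from baseline to the worst on-treatment value, and for a "Listing of all CTC grade 3 or 4 laboratory toxicities". SAP 5.3 uses sodium as its example of a test summarised separately by direction, so a hyponatremia summary is planned.

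**The concern.** In the other rows of the table, the lower bound of one grade is the upper bound of the next. The hyponatremia row drops one unit at two of its boundaries, from 130 to 129 and from 125 to 124. A value in either gap belongs to no grade, and the default then gives it the best grade available. A sodium of 124 would be tabulated as normal, while 125 is Grade 2 and 123 is Grade 3.

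The error understates laboratory toxicity in the graded summaries. It can also distort baselines: a subject who starts at 129 is entered as Grade 0, so a later value of 128 appears as a shift from Grade 0 to Grade 2.

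**Working it through.** The plan states no figure for this point, so there is none to reproduce. The check is to apply the printed row literally and compare it with a contiguous version.

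**Inputs (SAP 5.3).** A cell of the form < a - b is read as b ≤ x < a. LLN is 136 mmol/L. The default is Grade 0.

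**Step 1: grade individual values.**

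| Sodium (mmol/L) | Matching cell as printed | Grade after default | Grade if contiguous |
|---|---|---|---|
| 130 | Grade 1 | 1 | 1 |
| 129 | none | 0 | 2 |
| 128 | Grade 2 | 2 | 2 |
| 125 | Grade 2 | 2 | 2 |
| 124 | none | 0 | 3 |
| 123 | Grade 3 | 3 | 3 |
| 120 | Grade 3 | 3 | 3 |
| 119 | Grade 4 | 4 | 4 |

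At one decimal place, every value from 124.0 to 124.9 and from 129.0 to 129.9 falls to Grade 0. No other value is graded differently by the two versions.

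**Step 2: compare with other rows.** Low white cells, low platelets, low calcium, low magnesium, low glucose, high potassium and high sodium all have contiguous cut-offs. The hypernatremia row, directly above, runs to 150, then 150 to 155, then 155 to 160. Low sodium is the exception.

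**Step 3: share of a band affected.**

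- Whole numbers, equally frequent: 124 is one of 120, 121, 122, 123 and 124, so 1/5 = 20%. Likewise 129 is one of 125 to 129, so 20%.
- One decimal, equally frequent: 10 of the 50 values from 120.0 to 124.9, again 20%.
- Frequency falling by a ratio r for each mmol/L downwards (assumption): share at the top value = 1/(1 + r + r² + r³ + r⁴).
  - r = 0.9: 1/4.0951 = 24%
  - r = 0.8: 1/3.3616 = 30%
  - r = 0.7: 1/2.7731 = 36%

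The documents give no sodium distribution, so only the 20% equal-frequency count follows from the table alone. A steeper decline gives a larger share; r = 0.5 gives 52%.

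**Step 4: from values to subjects.** SAP 2.8.3 counts each subject once, at the worst post-baseline grade. A subject with values of 124 and 122 is still Grade 3. A subject with 124 and 126 is reported as Grade 2. A subject whose only low value is 124 is reported as Grade 0. The subject-level loss depends on repeat values and cannot be computed from the documents.

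**The case against.** The strongest objection is that the printed signs may not be reliable. The text of this table is visibly garbled in places: the neutrophil row is shifted by a column, and the albumin Grade 0 cell points the wrong way. The bands 129-125 and 124-120 also tile 120 to 129 exactly as whole numbers, so if the intended sign were ≤, whole-number results would have no gap. This is a fair reason to check the source table. It does not remove the defect. Both cells carry the same one-unit offset, the row above is contiguous, and with ≤ 129 and ≤ 124 a result such as 124.5 or 129.5 would still have no grade.

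A second objection is that the grading macro is not shown and may follow CTCAE directly. SAP 5.3 does refer to CTCAE version 5.0, but it then makes the printed table the operative criteria. The CTCAE extract in protocol Appendix 7 has no sodium row to fall back on. The Grade 0 cell also requires a value at or above LLN, which 124 fails, so the table and the default rule contradict each other. The footnote that lets Grades 1 to 4 overrule the normal range does not help where no grade cell applies.

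Third, the values do not disappear. SAP 2.8.3 lists all laboratory data and flags results below the reference range, so a sodium of 124 stays visible as low. That stands, and it limits the harm to the graded outputs.

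**Conclusion.** The row is wrong as written and should be corrected before the laboratory tables are programmed. Sodium from 129 to under 130 and from 124 to under 125 mmol/L is graded 0 under the stated rules. The size is one of five whole-number values in each band: 20% if equally frequent, 24-36% if frequency falls 10-30% per mmol/L. The comparison assumes that the intended grades are contiguous, which rests on the pattern of the other rows.

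A reader might go further in three ways that the documents do not support:

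- That a quarter to a third of Grade 3 hyponatremia is lost. This needs an assumed decline in frequency (r of about 0.74 to 0.89). It also concerns values rather than subjects, since anyone with another value of 123 or lower still counts as Grade 3 or 4.
- That the electrolyte AESI category is undercounted. SAP 2.8.1.1 derives AESI groupings from MedDRA-based searches of adverse events, and its grade filter applies to those events, not to this table.
- That efficacy is touched. No efficacy endpoint uses these grades.

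**What to change.** Make the hyponatremia row contiguous, in line with the other rows: Grade 1 < LLN - 130; Grade 2 < 130 - 125; Grade 3 < 125 - 120; Grade 4 < 120 mmol/L. Check the source table and confirm that the grading macro uses the same bounds. Add a program check that flags any sodium value below LLN that meets no grade, instead of letting it default to Grade 0.

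The cost is two numbers in the SAP table, any matching change in the macro, and one added check. No data collection or efficacy analysis changes.

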Based on the results achieved in other PRRT studies using ¹⁷⁷Lu-dotatate (Strosberg 2017; 2018 Brabander 2016), the major expected benefits to patients treated with Lutathera include the high probability of extending progression free survival, increasing overall survival and increasing time to deterioration of quality of life.

For this trial a 2:1 randomization design is chosen to allow patients to have a higher chance of getting the treatment which is anticipated to be more effective. For the same reason and to minimize the possible higher drop-out rate in the control arm, patients will be offered to cross-over to Lutathera after centrally confirmed RECIST progression (or locally confirmed if it occurs after Week 72 post the primary end point analysis).

The highest risks arising from treatment with Lutathera are radiation toxicities affecting either bone marrow or kidney function (Bergsma, et al., 2016a; Bergsma, et al., 2016b).

Kidney function risks are largely eliminated by the co-infusion of 2.5% Lys-Arg solutions during administration of Lutathera, which reduces the radiation dose to the kidney by approximately 45% (Rolleman, Valkema, Jong, Kooij, & Krenning, 2003). In the NETTER-1 trial no evidence of renal toxicities occurred within the period of observation (Strosberg, et al., 2017).

Bone marrow toxicity may occur in two forms: 1) acute toxicity that occurs after administration of Lutathera, during the treatment period; and 2) delayed toxicity that occurs in 1.5 to 2% of patients. The potential observed effects of short-term bone marrow toxicity are anemia, thrombocytopenia, and neutropenia which are usually mild and transient. In the NETTER-1 trial, grade 3 or 4 neutropenia, thrombocytopenia, and lymphopenia occurred in 1%, 2%, and 9% of patients (Strosberg, et al., 2017). Where hematological toxicity occurs, a trend towards stabilization followed by improvement in patients with longer follow-up is observed. It is important to note that the lymphocyte toxicity observed following PRRT is not a major concern regarding risk of infections, since only B lymphocytes are affected, a subtype which is not directly involved in infection defense (Sierra, et al., 2009).

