	Recurrent Grade 3 or 4	If AE resolves within 9 – 16 weeks after the previous dose, resume Lutathera at 3.7 GBq (100 mCi). If reduced dose does not result in Grade 3 or 4 anemia, administer Lutathera at 7.4 GBq (200 mCi) for next dose. If AE does not resolve within 16 weeks after the previous dose, permanently discontinue Lutathera. Permanently discontinue Lutathera.
Neutropenia	First occurrence of:	Withhold dose until complete or
	Grade 3 (ANC < 1.0 - 0.5 x 10 ⁹ /L) Grade 4 (ANC < 0.5 x 10 ⁹ /L)	If AE resolves before next planned Lutathera dose (i.e. within 9 weeks after the previous dose), administer next full dose of Lutathera (7.4 GBq / 200 mCi). If AE resolves within 9 – 16 weeks after the previous dose, resume Lutathera at 3.7 GBq (100 mCi). If reduced dose does not result in Grade 3 or 4 neutropenia, administer Lutathera at 7.4 GBq (200 mCi) for next dose. If AE does not resolve within 16 weeks after the previous dose, permanently discontinue Lutathera.
	Recurrent Grade 3 or 4	Permanently discontinue Lutathera.
Renal Toxicity	 First occurrence of: Creatinine clearance less than 40 mL/min; calculated using Cockcroft Gault formula with actual body weight, or 40% increase from baseline serum creatinine, or 40% decrease from baseline creatinine clearance; calculated using Cockcroft Gault formula with actual body weight. 	Withhold dose until complete resolution. If AE resolves before next planned Lutathera dose (i.e. within 9 weeks after the previous dose), administer next full dose of Lutathera (7.4 GBq / 200 mCi). If AE resolves within 9 – 16 weeks after the previous dose, resume Lutathera at 3.7 GBq (100 mCi). If reduced dose does not result in renal toxicity, administer Lutathera at 7.4 GBq (200 mCi) as next dose.

		If AE does not resolve within 16 weeks after the previous dose, permanently discontinue Lutathera.
	Recurrent renal toxicity Grade 3 or 4	Permanently discontinue Lutathera.
Hepatotoxicity	First occurrence of: Bilirubinemia greater than 3 times the upper limit of normal (Grade 3 or 4), or	Withhold dose until complete or partial resolution (Grade 0, 1 or 2). If AE resolves before next planned Lutathera dose (i.e. within 9 weeks after the previous dose), administer next full dose of Lutathera (7.4 GBq / 200 mCi).
		If AE resolves within 9 – 16 weeks after the previous dose, resume Lutathera at 3.7 GBq (100 mCi). If reduced Lutathera dose does not result in G3 or 4 bilirubinemia, administer Lutathera at 7.4 GBq (200 mCi) as next dose.

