Nephrotoxicity: Since Lutathera is cleared through the kidneys and reabsorbed by the kidneys, the kidneys have always been considered the "critical organs". An infusion of sterile amino acid is used for kidneys protection by inhibition of tubular reabsorption of Lutathera. Pursuant to these risk minimization efforts and in addition to the criteria of dose-modifying toxicities and criteria of inclusion (at baseline and before subsequent treatments) pertinent to renal function measurements, renal and urinary tract toxicities are considered AESI. Investigators must report as AESI renal toxicities, including renal failure (ranging from significantly reduced measured or estimated creatinine clearance to clinically overt renal failure other than that of obvious non-

IMP-induced origin), suspected radiation nephropathy of any type, such as radiation-induced thrombotic microangiopathy (manifested with, e.g., proteinuria, hypertension, edema, anaemia, decrease serum haptoglobin), or general symptoms and signs of acute radiation toxicity (e.g., increased frequency and urgency of urination, nocturia, dysuria, bladder spasm, bladder obstruction, genitourinary ulceration or necrosis).

Cardiovascular and electrolyte disorders: All clinically significant changes in blood pressure, heart rate, and electrocardiogram parameters must be reported as AESI if they occur within reasonable propinquity of Lutathera and/or amino acid administration in the judgment of the Investigator. Likewise, clinically manifest and/or consequences of hypo-/hypertension, arrhythmias, cardiac conduction disturbances, and other cardiac pathologies evidenced by objective findings / changes on electrocardiogram or echocardiography should also be considered for AESI reporting. In addition, any clinically significant event of hyperkalemia or hypokalemia must be reported as AESI.

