2.8.3 Laboratory data

The laboratory assessments require that blood samples for hematology and blood chemistry, and a urine sample for urinalysis are taken (see Table 8-2, Table 8-3, and Table 8-4 of the study protocol). Laboratory assessments will be performed at the investigational site.

The following laboratory parameters will be investigated and analyzed:

- (1) Haematology: White blood cells (WBC) with differential (i.e., Lymphocytes, Monocytes, Neutrophils, Eosinophils, Basophils), Platelets, Haemoglobin (Hb), Haematocrit, MCV
- (2) Blood chemistry: Blood urea nitrogen (BUN) or Urea, Serum creatinine, Uric acid, Albumin, Total bilirubin, ALP, AST/ASAT, ALT/ALAT, Gamma-GT, Sodium, Potassium, LDH, CgA (centralized assessment), Haemoglobin A1C (GlycoHb), fT4, Calcium, Magnesium, Fasting blood glucose, Thyrotropin, Creatinine clearance (calculated by the Cockroft-Gault formula)
- (3) Pregnancy test (if applicable)

On analyzing laboratory, data from all sources (central and local laboratories) will be combined. The summaries will include all assessments available for the lab parameter collected no later than 30 days after the last study treatment administration date (see [Section 2.1.1](#)). Separate

summaries will be generated for the randomized period, cross-over period, and re-treatment period.

Laboratory values outside normal ranges will be listed and flagged. The following flags will be used:

‘+’: ‘Higher than reference value’

‘-’: ‘Lower than reference value’

The respective parameter and the flagged value will be presented patient-wise by visit together with the reference values

The following summaries will be produced for hematology and biochemistry laboratory data (by laboratory parameter and treatment):

- Worst post-baseline CTC grade (regardless of the baseline status). Each subject will be counted only for the worst grade observed post-baseline.
- Shift tables using CTC grades to compare baseline to the worst on-treatment value
- For laboratory tests where CTC grades are not defined, shift tables using the low/normal/high/(low and high) classification to compare baseline to the worst on-treatment value.
- Box plots of laboratory values by scheduled time point.

The following listings will be produced for the laboratory data:

- Listings of all laboratory data, with CTC grades and classification relative to the laboratory normal range. Lab data collected during the post-treatment period will be flagged.

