ALT ↑	U/L	ALT	0 - 35 U/L or 0 - 0.58 kat/L ($60 \times \text{ukat}/L = U/L$)	≤ ULN	> ULN - 3.0 \times ULN	> 3.0 - 5.0 \times ULN	> 5.0 - 20.0 \times ULN	> 20.0 \times ULN	
Total bilirubin ↑	umol/L	BILI	5.1 - 20.5 umol/L or 0.3 - 1.2 mg/dL ($17.1 \times \text{mg/dL} = \text{umol/L}$)	≤ ULN	> ULN - 1.5 \times ULN	> 1.5 - 3.0 \times ULN	> 3.0 - 10.0 \times ULN	> 10.0 \times ULN	
Alk. Phosphatase ↑	U/L	ALP	36 - 92 U/L or 0.5 - 1.5 kat/L ($60 \times \text{ukat}/L = U/L$)	≤ ULN	> ULN - 2.5 \times ULN	> 2.5 - 5.0 \times ULN	> 5.0 - 20.0 \times ULN	> 20.0 \times ULN	
Creatinine ↑	umol/L	CREAT	61.9 - 115 umol/L or 0.7 - 1.3 mg/dL ($88.4 \times \text{mg/dL} = \text{umol/L}$)	≤ ULN	> ULN - 1.5 \times ULN	> 1.5 - 3.0 \times ULN	> 3.0 - 6.0 \times ULN	> 6.0 \times ULN	
Creatinine kinase↑	U/L	CK	30 - 170 U/L or 0.5 - 2.83 kat/L ($60 \times \text{ukat}/L = U/L$)	≤ ULN	> ULN - 2.5 \times ULN	> 2.5 - 5.0 \times ULN	> 5.0 - 10.0 \times ULN	> 10.0 \times ULN	
Albumin (Hypoalbuminemia)	g/L	ALB	35 - 55 g/L or 3.5 to 5.5 g/dL	≤ LLN	< LLN - 30 g/L	< 30 - 20 g/L	< 20 g/L	-	
Total Cholesterol ↑	mmol/L	CHOL	3.88 - 5.15 mmol/L or 150 - 199 mg/dL ($38.67 \times \text{mg/dL} = \text{mmol/L}$)	≤ ULN	> ULN - 7.75 mmol/L > ULN - 300 mg/dL	> 7.75 - 10.34 mmol/L > 300 - 400 mg/dL	> 10.34 - 12.92 mmol/L > 400 - 500 mg/dL	> 12.92 mmol/L > 500 mg/dL	
Lipase ↑	U/L	LIPASE	< 95 U/L or < 1.58 kat/L ($60 \times \text{ukat}/L = U/L$)	≤ ULN	> ULN - 1.5 \times ULN	> 1.5 - 2.0 \times ULN	> 2.0 - 5.0 \times ULN	> 5.0 \times ULN	
Amylase ↑	U/L	AMYLASE	0 - 130 U/L or 0 - 2.17 kat/L ($60 \times \text{ukat}/L = U/L$)	≤ ULN	> ULN - 1.5 \times ULN	> 1.5 - 2.0 \times ULN	> 2.0 - 5.0 \times ULN	> 5.0 \times ULN	
Uric acid (Hyperuricemia)	umol/L	URATE	150 - 470 umol/L or 2.5 - 8 mg/dL ($59.48 \times \text{mg/dL} = \text{umol/L}$)		Defined by clinical criteria only in CTCAE V5				

ULN = Upper Limit of Normal range; LLN = Lower Limit of Normal range

LAB - CTC grades in Novartis Oncology (26Jul18)

CTC grades for laboratory values in Novartis Oncology (based on CTCAE v5 – Nov 2017)

Page 2

CTC Grades ⁽¹⁾									
Lab test (toxicity)	SI unit	Lab test (NCDS)	Normal ranges (Merck manual, July 2015) and conversion factors	0	1	2	3	4	
Phosphorus (Hypophosphatemia)									
Phosphorus (Hypophosphatemia)	mmol/L	PHOS	0.97 - 1.45 mmol/L or 3.0 - 4.5 mg/dL ($0.32 \times \text{mg/dL} = \text{mmol/L}$)		Defined by clinical criteria only in CTCAE V5				

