Fibrinogen ↓	g/L	FIBRINO	1.5 - 3.5 g/L or 150 - 350 mg/dL ($0.01 \times \text{mg/dL} = \text{g/L}$)	≥ LLN	< LLN - 0.75 \times LLN	< 0.75 - 0.5 \times LLN	< 0.5 - 0.25 \times LLN	< 0.25 \times LLN	

ULN = Upper Limit of Normal range; LLN = Lower Limit of Normal range

(1) LAB CTC grades 1, 2, 3, 4 overrule the study specific (central or local) normal range criteria, e.g. if ULN of Sodium is 151 mmol/L and the value is 151 mmol/L, CTC grade 2 is assigned although the value is ≥ ULN.

Clinical criteria such as 'asymptomatic' or 'life-threatening consequences' are not considered for determination of LAB CTC grades. Concomitant usage of therapy is also not considered.

Values and LNrs for blood differentials can be given as %, absolute values should then be calculated using WBC. Generally, ≥ 1.5 \times 10⁹/L (lymphocytes) and ≥ 2 \times 10⁹/L (neutrophils) are considered as LAB CTC grade 0

The comparison with baseline is not considered for derivation of LAB CTC grades

Imputation Rules

CTC grading for blood differentials is based on absolute values. However, this data may not be reported as absolute counts but rather as percentage of WBC.

If laboratory values are provided as ‘<X’ (i.e., below limit of detection) or ‘>X’, prior to conversion of laboratory values to SI unit, these numeric values are set to X.

The following rules will be applied to derive the WBC differential counts when only percentages are available for a xxx differential

$$\text{xxx count} = (\text{WBC count}) * (\text{xxx \%value} / 100)$$

Further derivation of laboratory parameters might be required for CTCAE grading. For instance, corrected calcium can be derived using the reported total calcium value and albumin at the same assessment using the following formula:

$$\text{Corrected Calcium (mg/dL)} = \text{Calcium (mg/dL)} - 0.8 [\text{Albumin (g/dL)} - 4]$$

In order to apply the above formula, albumin values in g/L will be converted to g/dL by multiplying by 0.1, calcium values in mmol/L will be converted to mg/dL by dividing by 0.2495. For calculation of laboratory CTC grades 0 and 1, the normal range for derived corrected calcium is set to the same limits (in mg/dL) as for calcium.

CTC grades for the derived absolute WBC differential counts (neutrophils, lymphocytes) and corrected calcium will be assigned as described above for grading.

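### No planned laboratory table counts patients who meet the protocol's own renal thresholds, and a 40% creatinine rise from a normal baseline is graded only 0 or 1

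*SAP*

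**What the plan says.** Protocol 4.5 (Risks and benefits) gives the highest risks of Lutathera as "radiation toxicities affecting either bone marrow or kidney function". Table 6-4 (Protocol 6.5.2.1) sets three renal triggers: calculated clearance under 40 mL/min, or "40% increase from baseline serum creatinine, or 40% decrease from baseline creatinine clearance". The action at first occurrence is "Withhold dose until complete resolution". Footnote 3 to Table 8-2 applies the 40% rules in the Lutathera arm, requires a measured clearance when one is met, and allows treatment to continue if the measured fall is 40% or less.

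SAP 5.3 grades creatinine from a reference range of "61.9 - 115 umol/L or 0.7 - 1.3 mg/dL": Grade 0 up to ULN, Grade 1 up to 1.5 x ULN, Grade 2 up to 3 x ULN. It adds: "The comparison with baseline is not considered for derivation of LAB CTC grades". The grade table has no row for creatinine clearance.

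SAP 2.8.3 lists both serum creatinine and creatinine clearance for analysis. It plans worst post-baseline grade, grade shifts from baseline to worst value, and box plots by time point. For the rest it says: "For laboratory tests where CTC grades are not defined, shift tables using the low/normal/high/(low and high) classification". The same section uses multiples of the baseline value for liver tests in patients with raised transaminases at baseline.

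**The concern.** The protocol judges renal toxicity largely by change within the patient; the laboratory tables judge it by position relative to a normal range. A patient can therefore lose enough renal function to trigger the dose rule while the tables show little or nothing. A patient whose clearance is already low at baseline is shown as low to low after any further fall.

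At stake is how clearly the report can compare renal decline between arms. The efficacy analyses are not affected.

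**Working it through.** **Inputs.** ULN 115 umol/L, lower limit 61.9 umol/L, and the grade limits above (SAP 5.3). Triggers: creatinine x 1.4, clearance x 0.6, clearance under 40 mL/min (Protocol Table 6-4). Cockcroft-Gault constants: 1.23 for men, 1.04 for women (SAP 5.3). The range is internally consistent: 0.7 x 88.4 = 61.9 and 1.3 x 88.4 = 114.9.

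**Creatinine up 40%.** Let the baseline be b.
- Grade 0 if 1.4b <= ULN, so b <= 115/1.4 = 82.1 umol/L.
- At most Grade 1 if 1.4b <= 1.5 x ULN, so b <= 172.5/1.4 = 123.2 umol/L, or 1.07 x ULN.
- From the top of the normal range, 1.4 x 115 = 161, below 172.5: Grade 1.
- Above 1.07 x ULN it is Grade 2. For example, 130 x 1.4 = 182 = 1.58 x ULN.

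In multiples of ULN these limits hold whatever ULN a site uses: 1.4 x a normal value cannot exceed 1.4 x ULN, and Grade 2 begins above 1.5 x ULN.

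**Room for larger rises.** From 61.9 umol/L, creatinine can rise by 115/61.9 - 1 = 86% within Grade 0, and 172.5/61.9 = 2.79-fold before passing Grade 1.

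**Clearance down 40%.** With age and weight unchanged, creatinine is multiplied by 1/0.6 = 1.667.
- Grade 0 if b <= 0.6 x 115 = 69 umol/L.
- At most Grade 1 if b <= 0.9 x 115 = 103.5 umol/L.
- From 110 umol/L, 110/0.6 = 183 = 1.59 x ULN: Grade 2. This trigger can therefore reach Grade 2 from a normal baseline.

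**Clearance under 40 mL/min.** For an illustrative woman of 75 years and 50 kg, the threshold is crossed at creatinine (140 - 75) x 50 x 1.04/40 = 84.5 umol/L, which is Grade 0.

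**What one patient looks like.** Take an illustrative man of 65 years and 75 kg whose creatinine goes from 80 to 112 umol/L. This meets the 40% creatinine threshold. Clearance falls from 75 x 75 x 1.23/80 = 86.5 to 75 x 75 x 1.23/112 = 61.8 mL/min. The creatinine shift table records Grade 0 to Grade 0.

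**Other planned outputs.** Box plots show the distribution at each visit, not change within a patient. The nephrotoxicity grouping is rebuilt from coded adverse event terms (SAP 2.8.1.1), so it contains only what was reported.

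**The case against.** Kidney function is not left unexamined. Baseline shift tables and box plots are planned, Protocol 12.5.3 promises summary statistics by visit, and all laboratory values are listed. Nephrotoxicity is an adverse event of special interest with no grade floor in SAP Table 2.8-1. It is summarized by arm and has a time-to-first-occurrence analysis. Lutathera delays and modifications are tabulated with reasons (SAP 2.4.1.4). A reader might therefore infer too much from the gap, in three ways:

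- *That creatinine is never compared with baseline.* It is, as category shifts.
- *That the laboratory tables are the only fair comparison between arms.* The documents do not support this. Protocol 8.5.2 and 10.1.1 send clinically relevant laboratory changes to the adverse event page in both arms. Protocol 10.1.5 requires renal events of special interest in both arms, "ranging from significantly reduced measured or estimated creatinine clearance to clinically overt renal failure". Laboratory sampling is itself uneven: Protocol 8.5.2 adds pre-dose tests in the Lutathera arm.
- *That every threshold crossing ends Lutathera.* Table 6-4 withholds the dose at first occurrence, and footnote 3 to Table 8-2 can let treatment continue.

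All of this stands, and it limits the point without removing it. Event-based outputs depend on reporting, and the prompts to report differ. Under Protocol 10.1.1 a value that changes study medication becomes an adverse event, and the 40% rule can do that in the Lutathera arm. Control-arm dose adjustment (Protocol 6.5.2.2) is framed around Grade 3 or 4 toxicity and sets no renal threshold.

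**Conclusion.** The point holds as a gap in the laboratory summaries. No planned table counts patients who meet any of the three renal thresholds. Every rise that just meets the 40% creatinine threshold from a normal baseline is Grade 0 or 1, and it is Grade 0 with no shift for baselines up to ULN/1.4.

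The result has limits. It does not extend to baselines above 1.07 x ULN, to all larger rises, or to a 40% clearance fall from baselines above 103.5 umol/L. The umol/L figures assume the SAP's ULN of 115; site ranges may differ. The share of patients affected cannot be given, because the documents contain no baseline creatinine distribution. The patient examples are illustrative.

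This is a worthwhile, inexpensive improvement to safety reporting. Nothing here judges whether the renal dose rule is right.

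**What to change.** In SAP 2.8.3 add, by arm and treatment period, using the safety baseline in SAP 2.1.1.8:

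- the number (%) with a creatinine rise of at least 40% from baseline;
- the number (%) with a fall in calculated clearance of at least 40% from baseline;
- the number (%) with any post-baseline clearance below 40 mL/min;
- a shift table, baseline to worst, of clearance in bands: 60 or above, 40 to under 60, under 40 mL/min. The 60 cut-off is already used in SAP 2.2.3.

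Label these as laboratory thresholds met, not confirmed dose-modifying toxicities, because of the measured-clearance check in footnote 3 to Table 8-2.

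For the randomized period, show the counts a second time using only comparable scheduled visits in both arms. Otherwise the extra pre-dose samples give the Lutathera arm more chances to cross a threshold.

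The cost is one or two descriptive tables plus the restricted-visit repeat. Creatinine is already collected, and SAP 5.3 already derives clearance where the site value is missing. No dosing rule or efficacy analysis changes.
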